5.4 Planned Subgroups, Interactions, and Covariates

There are no planned subgroup analyses.

5.5 Derived and Computed Variables

The primary outcome for the study, response vs. non-response will be defined according to the following table.

Table 1: Response Table

Response Type	Definitions
Complete Response	Resolution of all manifestations of ocular GVHD 1. NIH CC eye score = 0 2. DEWS = 1
Partial Response (PR)	1. No worsening in NIH CC eye score 2. At least one point decrease in DEWS
Mixed Response	1a. Any decrease in the NIH CC eye score 1b. No improvement in DEWS. or 2a. Decrease in DEWS 2b. Worsening in the NIH CC eye score
No Response (NR)	No change in both the NIH CC score and the DEWS
Progressive Disease (PD)	Worsening on DEWS irrespective of NIH CC eye score

An eye will be coded as responding if it is categorized as CR or PR. All other situations, including MR, NR, and PD will be considered as not responding.

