5.4 Concomitant Medications and Procedures

Only medications with ocular effects will be recorded at screening and at subsequent study visits. These medications will be recorded in the medical record and appropriate CRF.

Patients may use non-medicated saline eye drops (artificial tears), provided they are applied in both eyes greater than 30 minutes following the application of the study eye drops.

All other eye drops, other than non-medicated saline eye drops, are prohibited while the patient is on study. If the patient is on medicated eye drops, a seven day washout is required before starting treatment. Patients can enroll if they have bilateral punctal plugs or if puncta were previously thermally cauterized, but the insertion of punctal plugs or cauterization is not allowed while the subject is on study.

5.5 Assessment of Response:

Assessment of response will be performed at 30 ± 3 , 60 ± 3 and 100 ± 3 days after initiation of therapy with pAF. The response is a combination of the NIH CC assessments and the ophthalmologic assessment (DEWS evaluation) as follows:

- NIH Consensus Conference (CC) for assessment of response in chronic GVHD
- Ophthalmologic assessment: Dry eye assessment will be performed over the course of four eye exams, including a baseline comprehensive eye exam (including a dilated fundus examination), and three follow-up exams (without dilation) on Day 30 ± 3 , Day 60 ± 3 and Day 100 ± 3 . Signs and symptoms of dry eye will be assessed at each exam using the grading scale provided by the International Dry Eye Workshop (DEWS) 2007 report.¹ DEWS assessment will include visual symptoms, severity and frequency of discomfort, conjunctival injection, conjunctival staining (using NaFl), corneal staining (using NaFl), corneal/tear signs (including filamentary keratitis and debris), the eyelids and meibomian glands, and fluorescein tear break-up time (TFBUT). Each sign/symptom will be graded on a scale of 1 to 4, with 4 being most severe. A total score will be taken at each exam, and a cumulative decrease in overall score >2 will constitute improvement with treatment. Note: Schirmer testing will not be performed or graded, as it has no proven value in ocular chronic GVHD.

Responders would be defined as a one point improvement in the dry eye grading scale (DEWS), without worsening in the eye score (NIH Consensus Criteria Ocular Assessment).

5.6 Assessment of Secondary Endpoints:

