2.2 Study Outcomes

2.2.1 Primary Outcome(s)

The primary outcome is the binary variable of complete or partial response to treatment (as defined by resolution or no worsening on the clinician- reported NIH CC eye score) and a decrease of at least one point on the DEWS.

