4 STUDY SUBJECTS AND ANALYSIS POPULATIONS

4.1 Eligibility

Patients will be eligible for enrollment if they meet all of the following inclusion criteria:

1. Patients with chronic GVHD \geq Grade II diagnosed within 3 years after hematopoietic stem cell transplant (HSCT) for any disease, with any graft, and any conditioning regimen with dry eye (patients may be using bilateral scleral lenses and/or bilateral punctal plugs at the time of accrual)
2. Patients who are 18 years of age or older.
3. Willing and able to provide informed consent.

Patients will be ineligible for enrollment if any of the following exclusion criteria are met:

- Patients who have any other reversible cause for dry eye at the time of accrual.
- More than 2 lines of therapy beyond corticosteroids with or without calcineurin inhibitors or sirolimus
- Relapsed malignancy after transplantation
- A difference in dryness between both eyes of more than 2 points of the grading provided by the International Dry Eye Workshop (DEWS) 2007 report
- Patients who are pregnant or plan to become pregnant while participating in the study.
- Patients who are not willing to discontinue the use of any eye drops, with the exception of non-medicated lubricant eye drops (artificial tears). All eye drops (excluding non-medicated lubricant eye drops) must be stopped at least seven days before treatment with pAF.
- Inability to comply with the investigational plan and visit schedule for any reason, in the judgement of the investigator.

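### SAP Table 1 defines Complete Response by end-state scores with no required DEWS decrease, so an eye at DEWS 1 at baseline can be both responder and non-responder, in conflict with SAP 2.2.1 and Protocol 5.5

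*SAP*

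**What the plan says.** The binary primary outcome is described in three places.

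- **SAP 5.5, Table 1.** Complete Response (CR) is headed "Resolution of all manifestations of ocular GVHD" and then given two numbered criteria, "1. NIH CC eye score = 0 2. DEWS = 1". Partial Response (PR) needs no worsening in the NIH score and "At least one point decrease in DEWS". The first form of Mixed Response (MR) is "1a. Any decrease in the NIH CC eye score 1b. No improvement in DEWS". No Response (NR) is "No change in both the NIH CC score and the DEWS". CR and PR are coded as responding, everything else as not responding. Nothing says which category wins when an eye fits two.
- **SAP 2.2.1.** The outcome is complete or partial response on the NIH score "and a decrease of at least one point on the DEWS".
- **Protocol 5.5.** "Responders would be defined as a one point improvement in the dry eye grading scale (DEWS), without worsening in the eye score".

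SAP 6.2.1 gives the NIH eye score as 0 to 3 and DEWS as 1 to 4, so DEWS 1 is the floor. Eligibility (Protocol synopsis, SAP 4.1) is judged per patient. The only between-eye limit is the exclusion of "A difference in dryness between both eyes of more than 2 points".

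**The concern.** CR is the only category in Table 1 whose numbered criteria are absolute scores; the other four are defined by change. An eye already at DEWS 1 cannot fall further. It can meet the CR criteria, but it can never respond under SAP 2.2.1 or Protocol 5.5.

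The primary McNemar test uses only discordant pairs, so the coding of one eye changes the data for the test. If the affected eye is the saline eye, coding it as a responder either removes a pair that favours pAF or creates one that favours saline. If it is the pAF eye, the shift goes the other way. SAP 5.6 calls for dual programming. Two programmers could each follow Table 1 faithfully and disagree, and the SAP gives no rule to settle it.

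**Working it through.** **1. The plan's own sample size.** Inputs from SAP 7: alpha 0.05 (taken as two-sided, since sidedness is not stated), 80% power, control response 5%, treated response 60% or 50%. The paired (Connor) formula, with the stated rates used directly as discordant proportions p10 and p01, pd = p10 + p01 and d = p10 − p01, is

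N = [1.96·√pd + 0.8416·√(pd − d²)]² / d²

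- 60% vs 5%: pd = 0.65, d = 0.55, N = 14.25, rounded up to 15.
- 50% vs 5%: pd = 0.55, d = 0.45, N = 18.77, rounded up to 19.

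Both stated sizes reproduce. They do not depend on Table 1, because the 5% control rate is an assumption of the plan.

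**2. Which eyes are affected.** There are 4 × 4 baseline states and 4 × 4 day-30 states, so 256 score paths. I classified each by Table 1 and by the rule in SAP 2.2.1 and Protocol 5.5 (DEWS falls by at least 1, NIH does not worsen). Exactly four paths meet the numbered CR criteria without a DEWS decrease:

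| Baseline NIH/DEWS | Day 30 | Table 1 categories met | SAP 2.2.1 and Protocol 5.5 |
|---|---|---|---|
| 1/1 | 0/1 | CR and MR | non-responder |
| 2/1 | 0/1 | CR and MR | non-responder |
| 3/1 | 0/1 | CR and MR | non-responder |
| 0/1 | 0/1 | CR (numbered criteria) and NR | non-responder |

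Every other path that meets CR also meets the decrease rule.

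**3. Can such eyes be enrolled?** There is no per-eye minimum on either scale, and the eyes may differ by up to 2 points. On the 1 to 4 grade, a patient with DEWS 3 in one eye and 1 in the other is eligible.

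**4. What one eye can do.** The exact two-sided McNemar p-value for B against C discordant pairs, with B > C, is 2·P(X ≥ B) for X ~ Binomial(B + C, 0.5).

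- 6-0: 2/64 = 0.031
- 5-0: 2/32 = 0.063
- 6-1: 2·(7 + 1)/128 = 0.125

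Start from 6-0 with the affected saline eye coded as a non-responder. Coding it as a responder gives 5-0 if its partner eye responded, or 6-1 if the partner did not. For an affected pAF eye the same coding can turn 5-0 into 6-0 (partner not responding) or 6-1 into 6-0 (partner responding).

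**5. Effect on power.** Assumptions: a fraction g of eyes *in both arms* starts and stays at NIH 0 and DEWS 1; eyes are independent; the test is exact, two-sided, at 0.05; other eyes respond at the planned rate p. Under CR coding an arm's response rate is g + (1 − g)p. If a DEWS decrease is required it is (1 − g)p. The discordant probabilities are pT(1 − pC) and pC(1 − pT). For g = 10% and n = 15, CR coding gives pT = 0.64 and pC = 0.145; with the decrease required, pT = 0.54 and pC = 0.045.

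| Scenario | g | Power, CR coding | Power, decrease required | Difference (points) |
|---|---|---|---|---|
| n = 15, 60% vs 5% | 0 | 85.3% | 85.3% | 0 |
| | 5% | 76.2% | 81.2% | 5.0 |
| | 10% | 67.6% | 76.5% | 8.9 |
| n = 19, 50% vs 5% | 0 | 83.1% | 83.1% | 0 |
| | 5% | 72.6% | 79.3% | 6.7 |
| | 10% | 63.0% | 74.9% | 11.9 |

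**The case against.** **Table 1 already excludes the unchanged eye.** A reader might infer that the plan credits response to an eye that starts and stays at NIH 0 and DEWS 1. The documents do not settle that. The CR cell opens with "Resolution of all manifestations of ocular GVHD", and resolution presupposes something to resolve; the same eye also fits NR word for word. This stands: such an eye could be coded as a responder, but the wording points toward No Response. It does not help the other three paths. A fall in NIH from 1, 2 or 3 to 0 at DEWS 1 is resolution in the ordinary sense, and it still meets MR and still fails SAP 2.2.1 and Protocol 5.5.

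**Precedence is implied.** CR is listed first and non-response is the remainder, so CR might be taken to win. But MR and NR are named as non-response, and letting CR win would deepen the conflict with the other two sections.

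**Affected eyes will be rare.** Patients must have symptomatic disease and SAP 6.2.1 treats NIH 0 as asymptomatic, so this is probably right. The criteria apply per patient, though, so one clear eye is possible. No passage supports any particular frequency.

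**The power loss could look much larger.** Placing the affected eyes in the saline arm only (saline response 0.05 + 0.95g) would take power at g = 10% from 85% to 59% (n = 15) and from 83% to 51% (n = 19). That is not a fair measure. Eyes are randomised, so pAF eyes start at the floor equally often. The right comparison is also with the corrected rule, which does not restore 85% or 83%, because an eye at the floor cannot respond.

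**The DEWS scale is itself unsettled.** Protocol 5.5 also describes a total over several items, each graded 1 to 4, on which DEWS = 1 cannot occur. This stands. The overlap exists on the SAP's 1 to 4 grade.

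**Conclusion.** The inconsistency is real and should be corrected. On the SAP's 1 to 4 DEWS grade, four score paths satisfy the numbered CR criteria and also a category coded as non-response, and all four are non-response under SAP 2.2.1 and Protocol 5.5. The firm case is baseline DEWS 1 with NIH 1 to 3 falling to 0; the unchanged 0/1 eye is the weaker one.

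The practical size is uncertain and probably modest. One eye can move the result across 0.05 in either direction, depending on which eye is affected. The 5 to 12 point power difference rests on assumed frequencies of 5% and 10% in both arms and on independent eyes. The stated sample sizes of 15 and 19 are not affected.

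**What to change.** Before unblinding, add a third criterion to the Complete Response row of SAP Table 1: *and at least a one point decrease in DEWS from baseline*. Table 1, SAP 2.2.1 and Protocol 5.5 then give one responder rule, and all four overlapping paths become non-response. State that the rule applies to the SAP's 1 to 4 DEWS grade, and reconcile that grade with the total score in Protocol 5.5.

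The cost is a short change of wording. The downside should be stated in the SAP: an eye at DEWS 1 at baseline can never respond, even if its NIH score resolves. Giving CR explicit precedence would also remove the overlap inside Table 1, but SAP 2.2.1 and Protocol 5.5 would then have to change to match.

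A sensitivity analysis excluding pairs in which either eye has baseline DEWS 1 is optional and supportive only, because it drops whole pairs from a trial of 15 to 20 patients.

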5.6 Independent Review

All statistical analyses for primary reporting of trial results will be independently verified through dual programming. Two statisticians will each program all datasets and analyses

for the DSMB reports and the primary manuscript(s) and the results will be compared. This process will begin at the analysis design stage and will continue through writing of abstracts and manuscripts.

6 PLANNED ANALYSES

6.1 Description of Subject Characteristics

Publication of the primary results will include reporting of key baseline characteristics overall. These will include, but are not limited to

- gender
- race
- age
- baseline FACT-G
- baseline NIH CC eye score for each eye
- baseline DEWS for each eye
- baseline patient reported pain level for each eye
- baseline visual acuity for each eye

6.2 Primary Outcome Analysis

6.2.1 Response Table

The outcome is the combination of two measures, the NIH CC criteria and DEWS. Each will be summarized at 30, 60, and 100 days.

The NIH CC is a four level ordinal score ranging from 0 to 3 with 0 being asymptomatic and 3 being the worst possible. Treatment and control eyes will be summarized at baseline and each visit using counts and percentages. At each visit we will summarize the number and percent of treatment and control eyes that have improved, stayed the same, and progressed compared to baseline. An improvement will be defined as movement to a lower score and symptom progression will be defined as movement to a higher score.

The DEWS is a four level ordinal score ranging from 1 to 4 with 1 being asymptomatic to mild and 4 being the severe. Similar to the NIH CC score, treatment and control eyes will

be summarized at baseline and each visit using counts and percentages. At each visit we will summarize the number and percent of treatment and control eyes that have improved, stayed the same, and progressed compared to baseline. An improvement will be defined as movement to a lower score and symptom progression will be defined as movement to a higher score.

Analysis of the primary endpoint will be coded as each eye having responded or not responded at the 30 day visit. Because a participant's eyes are more likely to be similar compared to eyes from two different participants we will conduct a paired analysis using McNemar's test, as implemented in PROC FREQ, by constructing the following table where A is the number of participants who had both eyes respond; B is the number of participants who responded in the active eye but not in the control eye; C is the number of participants who did not respond in the active eye but responded in the control eye; and D is the number of participants who did not respond in either eye. pAF will be deemed to be effective if B is significantly greater than its expected value. If the observed table from the trial is sparse we will utilize the exact version of the McNemar's test.

Table 2: Outcome Table

		Control Eye	
		Responding	Not Responding
Active Eye	Responding	A	B
	Not Responding	C	D

6.3 Secondary Outcome(s) Analyses

6.3.1 NIH Consensus Criteria Ocular Score of Chronic GVHD

The NIH CC will be summarized as above. At each follow-up visit, 30 days, 60 days, and 100 days, the percent of treated eyes that have improved and progresses will be summarized using 95% confidence intervals. To test for a change within participants a sign test will be conducted. An improvement in an eye will be coded as a +1, symptom progression in an eye will be coded as -1, and no change coded as 0. A score will be created for each participant by subtracting the control eye from the treatment eye. Given the sample size it is likely we will use an exact binomial p-value.

6.3.2 Dry Eye Severity Grading Scheme (DEWS)

The DEWS will be summarized as above. At each follow-up visit, 30 days, 60 days, and 100 days, the percent of treated eyes that have improved and progressed will be summarized using 95% confidence intervals. To test for a change within participants a sign test will be conducted. An improvement in an eye will be coded as a +1, symptom progression in an eye will be coded as -1, and no change coded as 0. A score will be created for each participant

by subtracting the control eye from the treatment eye. Given the sample size it is likely we will use an exact binomial p-value.

6.3.3 Functional Assessment of Cancer Therapy - General (FACT G)

The FACT-G will be summarized at baseline at the 30, 60, and 90 day follow-up visits using medians and interquartile ranges. The overall FACT-G is calculated by scoring the individual subsections and then deriving an overall score (we need the manual to do this). FACT-G will not be normalized to a 0 - 100 range. A Wilcoxon signed-rank test will be calculated to compare change from baseline at each visit by subtracting the follow-up visit score from the baseline score.

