7 Data Management	17
7.1 Clinical Site Data Management	17
7.2 Electronic Data Capture System	17
7.3 Study Monitoring	17
7.3.1 Site Monitoring Plan	18
7.3.2 Clinical Site Monitoring	18
8 Data Coordinating Center	18
8.1 Security and Confidentiality	19
8.2 Record Access	20
9 Bibliography	20

List of Tables

1 List of Peptides according to their function	11
2 Schedule of Events	13

1 Synopsis

Title	A Randomized, Double-blinded, Placebo-Controlled Study for the Treatment of Ocular Chronic GVHD with Processed Amniotic Fluid (pAF) Drops
Short Title	pAF for the treatment of Ocular GVHD
IRB Number	00103515
IND	18489
Phase	I/II
Design	This is a randomized, double-blinded, placebo-controlled study of the efficacy of pAF in patients with hematologic malignancies who have undergone Allogeneic Hematopoietic Stem Cell Transplantation (HSCT) and are diagnosed with chronic GVHD of the eye.
Study Duration	Two years
Study Center(s)	University of Utah
Objectives	
Primary Objectives:
 
 • To determine the safety of pAF in patients with chronic ocular GVHD. • To determine the clinical effects of pAF in patients with chronic ocular graft versus host disease. 
Secondary Objectives:
 
 • To determine the change in National Institutes of Health (NIH) Consensus Criteria (CC) ocular score of chronic GVHD at 30 ± 3 days, 60 ± 3 days, and 100 ± 3 days from baseline related to the administration of pAF. • To determine change in Functional Assessment of Cancer Therapy-General (FACT G) (Quality of Life (QOL)) at 30 ± 3 days, 60 ± 3 days, and 100 ± 3 days related to the administration of pAF. • To determine changes in visual acuity related to the administration of pAF. • To determine the effects of pAF on the corneal surface. • To determine the changes in dry eye symptoms using the grading provided by the International Dry Eye Workshop (DEWS) 2007 report.¹ • To determine the changes in patient reported pain level related to the administration of pAF using the 0–10 pain rating scale during the first 60 days of the study.

Continued on next page

Continued from previous page

Number of Subjects	15–20 patients

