Statistical Methodology	
This is randomized, double-blinded, placebo-controlled study.
 
The clinical effects of pAF will be analyzed using descriptive statistics, Wilcoxon rank sum, and Fisher's exact test where applicable. Test for a significant response will be carried out using McNemar's test.
 
The proportion of subjects who experience adverse events and serious adverse events will be summarized descriptively; no inferential tests will be performed.

2 Objectives

Primary Objectives:

1. To determine the safety of pAF in patients with chronic ocular GVHD.
2. To determine the clinical effects of pAF in patients with chronic ocular GVHD.

Primary Endpoint:

1. Overall response (Complete Response & Partial Response) as defined in section 5.

Secondary Objectives and Endpoints:

1. To determine the change in National Institutes of Health (NIH) Consensus Criteria (CC) ocular score of chronic GVHD at 30 ± 3 days, 60 ± 3 days, and 100 ± 3 days from baseline related to the administration of pAF
2. To determine change in FACT G (QOL) at 30 ± 3 days, 60 ± 3 days, and 100 ± 3 days related to the administration of pAF.
3. To determine changes in visual acuity related to the administration of pAF.
4. To determine the effects of pAF on the corneal surface.
5. To determine the changes in dry eye symptoms related to the administration of pAF using the grading provided by the International Dry Eye Workshop (DEWS) 2007 report.¹
6. To determine the changes in patient reported pain level related to the administration of pAF using the 0–10 pain rating scale during the first 60 ± 3 days of the study.

3 Rationale and Background

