3 STUDY DESIGN AND METHODS

3.1 Overall Study Design

This is a randomized, double-blinded, placebo-controlled study of the efficacy of pAF in patients with hematologic malignancies who have undergone Allogeneic Hematopoietic Stem Cell Transplantation (HSCT) and are diagnosed with chronic GVHD of the eye. Patients will be allowed to continue the use of non-medicated lubricant eye drops (artificial tears) for ocular GVHD treatment prior to participating in this study. Patients are allowed to resume the use of eye drops after the 30 day treatment period at the discretion of the treating physician.

Participants will serve as their own control. A person will have one eye randomized to receive pAF and the other eye will receive saline drops.

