5.3 Multiple Comparisons and Multiplicity

As there is a single primary endpoint for this study, adjustment for multiple comparisons will not be required for the primary analysis.

For the secondary efficacy endpoints, a Bonferroni-Holm stepdown test will be used for assessing significance, with a total alpha level of 0.05 for these two outcomes.

Safety outcomes for this study will be reported using unadjusted p- values for each individual comparison. However, all reports of these outcomes, to the DSMB and in published reports, will explicitly note that multiple safety outcomes have been evaluated. Formal multiplicity-adjusted significance assessments for these outcomes will be performed upon request of the DSMB or other reviewers. The Bonferroni-Holm procedure will be used for such assessments.

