7 SAMPLE SIZE DETERMINATION

Analysis of the primary endpoint will be coded as each having responded or not responded at the 30 day visit. Because a participants eyes are more likely to be similar compared to eyes from two different participants we will conduct a paired analysis using McNemars test. Assuming a significance level of 0.05, and a response rate in the control eye of 5%, 15 participants will provide 80% power to detect a difference if the response in the treated eye is 60%. With 19 participants we will have 80% power to detect a response rate of 50%. Due to the small sample size it is likely an exact p-value will be calculated.

8 References

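### FACT-G has no comparator in this paired-eye design, so the planned change-from-baseline test cannot show a change attributable to pAF

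*SAP*

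**What the plan says.** The randomized unit is the eye. SAP 3.1 states: "Participants will serve as their own control", with one eye assigned to pAF and the other to saline.

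The FACT-G objective in protocol section 2 begins "To determine change in FACT G (QOL) at", names Days 30, 60 and 100, and ends by tying the change to pAF. The protocol synopsis and SAP 2.1.2 word it in the same way. SAP 2.2.2 lists FACT-G change among six secondary outcomes, and SAP 4.2.2 treats analyses of secondary outcomes as efficacy analyses.

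For the analysis, SAP 6.3.3 says: "A Wilcoxon signed-rank test will be calculated to compare change from baseline at each visit". Protocol section 6 names no FACT-G test. On multiplicity, SAP 5.3 says: "For the secondary efficacy endpoints, a Bonferroni-Holm stepdown test will be used for assessing significance". The same sentence then speaks of two outcomes and names neither.

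**The concern.** The design controls for whatever affects both eyes of a person by comparing one eye with the other. That protection needs a measurement on each eye. FACT-G is measured on the whole person, and every person is exposed to both products, so the saline eye cannot act as its control and no other comparator is planned.

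The objective asks whether pAF changed quality of life. The planned test asks whether quality of life differed from baseline. If the result is significant, the reader has a p-value listed under an objective that it does not address, and neither document warns that it is uncontrolled.

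**Working it through.** **1. Level of measurement.** The SAP 6.1 baseline list gives NIH CC eye score, DEWS, pain and visual acuity per eye. It gives FACT-G once, without that qualifier.

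**2. Contrast used for each secondary outcome.**

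| Outcome | SAP section | Quantity tested |
|---|---|---|
| NIH CC eye score | 6.3.1 | treated-eye minus control-eye change score |
| DEWS | 6.3.2 | treated-eye minus control-eye change score |
| FACT-G | 6.3.3 | baseline minus follow-up, one group |
| Visual acuity | 6.3.4 | treated-eye minus control-eye change |
| Corneal surface | 6.3.5 | treated-eye minus control-eye change score |
| Pain | 6.3.6 | treated-eye minus control-eye slope |

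Five of the six use the randomized contrast; FACT-G does not.

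**3. What the FACT-G change contains.** Write the mean change as pAF effect + everything else. The test addresses the sum. Non-pAF terms that the documents themselves supply are the seven-day washout of medicated drops (protocol 5.4), saline in the other eye (protocol 5.1) and eye drops that may be resumed after the 30-day treatment period (protocol section 5), before two of the three follow-up assessments. Regression to the mean and the course of systemic disease are further general possibilities.

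**4. The plan's own figures, used here only for n.** The protocol synopsis plans "15–20 patients". SAP section 7 says: "Assuming a significance level of 0.05, and a response rate in the control eye of 5%, 15 participants will provide 80% power" for a 60% treated-eye response, and gives 19 participants for 50%. Use the McNemar normal approximation n = (1.96√s + 0.8416√(s − d²))² / d², where s is the sum and d the difference of the two discordant probabilities. Assume a two-sided test and no participant with both eyes responding.

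- 60% vs 5%: s = 0.65, d = 0.55, n = 14.25, so 15.
- 50% vs 5%: s = 0.55, d = 0.45, n = 18.77, so 19.

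Both figures reproduce. They concern the eye-level primary endpoint and do not bear on FACT-G.

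**5. Illustration for FACT-G.** The drift and the normal distribution of changes are assumptions. The true pAF effect is set to zero. The test is the exact two-sided signed-rank test at an unadjusted 0.05, with 20,000 simulated trials per cell. Drift is in SDs of the change score.

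| n | 0 | 0.2 SD | 0.3 SD | 0.5 SD | 0.8 SD |
|---|---|---|---|---|---|
| 15 | 4.7% | 10.5% | 18.4% | 41.9% | 80.7% |
| 19 | 4.8% | 13.0% | 23.0% | 52.7% | 89.8% |
| 20 | 4.8% | 13.1% | 23.5% | 54.2% | 91.1% |

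For at least one of three visits, unadjusted and with an assumed between-visit correlation of 0.5, the figure is about 12% with no drift. With a 0.5 SD drift it is 68% (n = 15) or 78% (n = 19).

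**6. The same drift in an eye-level contrast.** Give both eyes a shared change with mean 0.5 and SD 0.7, plus independent noise of SD 0.7 per eye. One eye's change then has SD √(0.49 + 0.49) = 0.99, so the drift is about 0.5 SD. Testing one eye against zero rejects in 42.7% (n = 15) and 53.2% (n = 19) of trials. Testing the difference between eyes rejects in 5.0% and 4.8%.

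**7. Multiplicity adjustment.** With a 0.5 SD drift, the first Holm step for two outcomes (0.05/2 = 0.025) gives 28.8% (n = 15) and 39.1% (n = 19). The first step for six outcomes (0.05/6 = 0.0083) gives 14.9% and 24.4%. A stricter threshold lowers the rate without supplying a comparator.

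**The case against.** The signed-rank test is valid for the question of whether FACT-G changed, and SAP 6.3.3 claims no more than that. The only rule for declaring pAF effective is in SAP 6.2.1 and concerns the primary McNemar table. SAP 1.1 calls the study a pilot collecting preliminary data. All of this stands. A reader might infer that a significant FACT-G result would be wrongly credited to pAF, but the documents do not say how it would be interpreted. They support only the statement that it could not be attributed to pAF.

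A reader might also infer from SAP 5.3 that FACT-G takes a place in the Holm family at the expense of the eye-level outcomes. The documents do not show this: the two outcomes are unnamed while six are listed.

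The simulated percentages are the power to detect a real change of an assumed size. They are not false-positive rates for the hypothesis tested, which stays near 5% per visit when nothing drifts. Some sources of drift are also weak. Artificial tears are permitted before and during the study, so they are not clearly a change from baseline, and resumed drops bear mainly on Days 60 and 100.

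Finally, a confidence interval would often exclude zero under the same drift, so replacing the p-value does not by itself settle attribution. That is correct: the label and the reworded objective do that work. What the objection leaves untouched is the mismatch between the objective, the efficacy status given to secondary outcomes, and a test without a comparator.

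**Conclusion.** The point holds. As written, the FACT-G analysis cannot answer its objective, because the design offers no comparator for a person-level score. This follows from the documents alone and needs no assumption about drift.

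How often an unrelated change would reach significance is not known. The range runs from about 5% per visit with no drift to 42–53% with a 0.5 SD drift (n = 15 to 19, unadjusted, normal changes, zero pAF effect), and it is illustrative only. The point is limited to one secondary outcome. It does not touch the primary analysis, the other five secondary contrasts or the sample size, and it does not rest on FACT-G being in the Holm family.

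**What to change.** - **SAP 6.3.3:** replace the signed-rank test with median FACT-G change and a confidence interval at each scheduled visit. Label it as uncontrolled, participant-level description with no efficacy p-value. The section gives the last visit as Day 90 while the objective and schedule give Day 100; reconcile this in the same edit.
- **Protocol synopsis, protocol section 2 and SAP 2.1.2:** remove the closing words of the FACT-G objective that tie the change to pAF.
- **SAP 5.3:** state that FACT-G is not in the Holm family. This is needed because the section does not name its two outcomes.

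The cost is wording changes in both documents and the loss of a FACT-G p-value. Data collection, visits and sample size are unchanged, and FACT-G is still reported.
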